8.3.2.3 Cardiovascular risk factor assessment

Cardiovascular events (CVE) including ischemic heart disease, peripheral arterial occlusive disease and ischemic cerebrovascular events have been reported in CML patients receiving TKI therapies as specified in Table 8-1. Since the study treatment in the trial is TKIs (asciminib), the cardiovascular risk factors (hypertension, tobacco use, raised blood glucose (diabetes), physical inactivity, unhealthy diet, cholesterol/lipids, overweight and obesity) of each patient will be collected prior to randomization and end of treatment. This will also include the patients Family History.

8.3.2.4 Pulmonary function test

Pulmonary function test will only be performed if clinically indicated by treating physician. The pulmonary function test with the plethysmograph includes the assessment of the lung volumes FEV1, FVC, FEV1/FVC, TLC and VC. In addition the DLCO to evaluate the gas exchange will be assessed at the same time of testing if indicated. Any clinically significant findings will be collected and reported in the database (i.e. reported as adverse events).

8.3.3 Pregnancy and assessments of fertility

All women of childbearing potential have to complete a serum pregnancy test at the screening visit, at every monthly visit until end of treatment visit. Pregnancy testing is not required for patients who are determined to be post-menopausal. The time windows granted for pregnancy testing are identical with the corresponding visit time windows for each visit. Refer to [Table 8-1](#) and [Table 8-6](#) of the Visit evaluation schedules. Serum pregnancy test will be performed by a central laboratory.

Pregnancies diagnosed in female patients participating in the study (including female partners of male patients) should be recorded on a Clinical Trial Pregnancy Form and reported by the investigator to the Oncology Novartis Chief Medical Office and Patient Safety (CMO&PS) Department.

During the whole study, women of childbearing potential should employ the use of highly effective contraception. Highly effective contraception methods are defined in [Section 5.2](#).

Sexually active males on asciminib treatment must use a condom during intercourse while taking the drug and for at least 3 days after stopping treatment and should not father a child within this period. A condom is required to be used also by vasectomized men in order to prevent delivery of the drug via seminal fluid. In addition, male participants must not donate sperm for the time period specified above.

8.3.4 Other safety evaluations

Not Applicable

8.3.5 Appropriateness of safety measurements

The safety assessments selected are standard for this indication/participant population.

8.4 Efficacy

8.4.1 Molecular Response

Molecular response (MR) BCR-ABL1 will be assessed in all patients assigned Cohort A, B and C. The molecular response for all patients are to be assessed centrally.

Levels of BCR-ABL1 transcripts will be determined by real-time quantitative PCR (RQ-PCR) testing of peripheral blood and analyzed at a central testing laboratory. Log reduction in BCR-ABL1 transcripts levels from the standardized baseline value, or the percent ratio of BCR-ABL1 transcripts versus control gene (ABL) transcripts converted to a reference standard, international scale ([Hughes and Branford 2006](#)), will be calculated for each sample.

MR2 and related variables are defined as the following:

- Rate of MR2 where MR2 is defined as a ≥ 2 log reduction in BCR-ABL1 transcripts compared to the standardized baseline equivalent to $\leq 1\%$ BCR-ABL1/ABL % by international scale as measured by RQ-PCR, confirmed by duplicate analysis of the same sample
- Time to MR2 defined as the time from the date of start of study treatment to the date of the first documented MR2
- Duration of MR2 defined as the time from the date of first documented MR2 to the earliest date of loss of MMR, progression to AP or BC, or CML-related death

Major molecular response (MMR) and related variables are defined as the following:

- Rate of Major Molecular Response (MMR) where MMR is defined as a ≥ 3.0 log reduction in BCR-ABL1 transcripts compared to the standardized baseline equivalent to $\leq 0.1\%$ BCR-ABL1/ABL % by international scale as measured by RQ-PCR, confirmed by duplicate analysis of the same sample
- Time to MMR defined as the time from the date of start of study treatment to the date of the first documented MMR,
- Duration of MMR defined as the time from the date of first documented MMR to the earliest date of loss of MMR, progression to AP or BC, or CML-related death.

MR4 and related variables are defined as the following:

- Rate of MR4 where MR4 is defined as a ≥ 4 log reduction in BCR-ABL1 transcripts compared to the standardized baseline equivalent to $\leq 0.01\%$ BCR-ABL1/ABL % by international scale as measured by RQ-PCR, confirmed by duplicate analysis of the same sample
- Time to MR4 defined as the time from the date of start of study treatment to the date of the first documented MR4,
- Duration of MR4 defined as the time from the date of first documented MMR to the earliest date of loss of MR4, progression to AP or BC, or CML-related death.

MR4.5 and related variables are defined as the following:

- Rate of MR4.5 where MR4.5 is defined as a ≥ 4.5 log reduction in BCR-ABL1 transcripts compared to the standardized baseline equivalent to $\leq 0.0032\%$ BCR-ABL1/ABL % by international scale as measured by RQ-PCR, confirmed by duplicate analysis of the same sample
- Time to MR4.5 defined as the time from the date of start of study treatment to the date of the first documented MR4.5
- Duration of MR4.5 defined as the time from the date of first documented MMR to the earliest date of loss of MR4.5, progression to AP or BC, or CML-related death

Loss of Responses

Loss of MR2 is defined as increase of BCR-ABL1/ABL to $> 1\%$ by international scale (IS). BCR-ABL less than 1% according to the IS can be regarded as an equivalent to CCyR. Loss of MR2 must be confirmed by subsequent sample analysis within 4 to 6 weeks.

Loss of MMR is defined as increase of BCR-ABL1/ABL to $> 0.1\%$ by international scale (IS) in association with a ≥ 5 -fold rise in BCR-ABL1 from the lowest value achieved on study treatment and replicated by a second analysis of the same sample. Loss of MMR must be confirmed by subsequent sample analysis within 4 to 6 weeks showing loss of MMR associated with a ≥ 5 -fold rise in BCR-ABL1 from the lowest value achieved on study treatment, unless it is associated with confirmed loss of CHR to AP/BC or CML-related death.

Mutational Analysis (T315I mutation)

Mutational analysis will be performed at a Novartis designated laboratory by Sanger sequencing for T315I mutation at Screening if T315I mutational analysis is not confirmed and upon confirmed loss of MMR and/or at end of treatment. Please see [Section 8.5.3](#).

The blood samples will be taken as described in [Table 8-1](#), and [Table 8-6](#).

Table 8-3 Blood samples (efficacy secondary endpoint)

| Sample Type | Volume | Visit | Time point |
|---|--|--|------------|
| Blood for BCR-ABL1 quantification by RQ-PCR | 20 mL | Screening/Baseline | Pre-dose |
| | 20 mL | Week 4 | Pre-dose |
| | 20 mL | Week 12 | Pre-dose |
| | 20 mL | Week 24 | Pre-dose |
| | 20 mL | Week 36 | Pre-dose |
| | 20 mL | Week 48 | Pre-dose |
| | 20 mL | Week 60 ^β | Pre-dose |
| | 20 mL | (Week 72) End of Treatment | Anytime |
| Blood for BCR-ABL1 Mutation analysis by Sanger Sequencing | 5 mL | Screening | Pre-dose |
| | No sample collected - testing is performed on the "Blood for BCR-ABL1 quantification by RQ-PCR" sample | Upon confirmed loss of MMR and/or End of Treatment | Anytime |

β = only applicable if the visit is in-person

During the study, peripheral blood samples will be collected into PAXgene™ Blood RNA tubes for all RQ-PCR assessments. Detailed instructions for the collection, handling, and shipment of RQ-PCR and mutation samples are outlined in the [\[CABL001AUS04 Laboratory Manual\]](#).

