5.1 Inclusion criteria

Participants eligible for inclusion in this study must meet **all** of the following criteria:

1. Written informed consent must be obtained and signed prior to participation in the study
2. Male or female patients with a diagnosis of CML-CP ≥ 18 years of age
3. Patients must meet all of the following laboratory values at the screening visit:
 - $< 15\%$ blasts in peripheral blood or bone marrow
 - $< 30\%$ blasts plus promyelocytes in peripheral blood or bone marrow
 - $< 20\%$ basophils in the peripheral blood
 - $\geq 50 \times 10^9/L$ ($\geq 50,000/mm^3$) platelets
 - Transient prior therapy related thrombocytopenia ($< 50,000/mm^3$ for ≤ 30 days prior to screening) is acceptable
 - No evidence of extramedullary leukemic involvement, with the exception of hepatosplenomegaly
4. Mutation Analysis testing performed at screening.
5. Prior treatment with a minimum of:
 - 2 prior ATP-site TKIs (i.e. imatinib, nilotinib, bosutinib, dasatinib or ponatinib) in case of absence of T315I mutation
 - 1 prior ATP site TKI (i.e. imatinib, nilotinib, bosutinib, dasatinib or ponatinib) in case of presence of T315I mutation
6. Failure (adapted from the 2020 ELN Recommendations) or intolerance to the most recent TKI therapy at the time of screening
 - Failure for CML-CP patients (CP at the time of initiation of last therapy) is defined as meeting at least one of the following criteria.
 - Three months after the initiation of therapy: $>10\%$ BCR-ABL1 on International Scale (IS) if confirmed within 1-3 months
 - Six months after the initiation of therapy: BCR-ABL1 ratio $> 10\%$ IS
 - Twelve months after initiation of therapy: BCR-ABL1 ratio $> 1\%$ IS
 - At any time after the initiation of therapy, loss of CHR, MR2
 - At any time after the initiation of therapy, the development of new BCR-ABL1 mutations which potentially cause resistance to current treatment
 - At any time 12 months after the initiation of therapy, BCR-ABL1 ratio $\geq 1\%$ IS or loss of MMR
 - At any time after the initiation of therapy, new clonal chromosome abnormalities in Ph+ cells: CCA/Ph+
 - Intolerance is defined as:
 - Non-hematologic intolerance: Patients with grade 3 or 4 toxicity while on therapy, or with persistent grade 2 toxicity, unresponsive to optimal management, including dose adjustments (unless dose reduction is not considered in the best interest of the patient if response is already suboptimal)

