8.1 Screening

Molecular pre-screening

Not Applicable

Screening

Written informed consent must be obtained before any study specific medical procedures are performed. All screening/baseline assessments should occur within 21 days before Week 1 Day 1.

During the screening visit, inclusion and exclusion criteria will be assessed. Screening assessments to confirm eligibility must be performed prior to randomization. The results of the real time quantitative polymerase chain reaction (RQ-PCR) must be available prior to randomization and first dose of study treatment.

For details of assessments required during screening please refer to [Table 8-1](#).

Laboratory baseline assessments (including hematology, chemistry and serum pregnancy test), physical examination including extramedullary involvement, performance status, ECG, height, weight and vital signs, evaluation of all relevant medical history including cardiovascular risk factors, CML disease history, including prior TKI therapy and antineoplastic medication and prior and concomitant medication must be performed prior to the first dose of study treatment. Patients with potassium, and/or magnesium and/or total calcium levels that are < LLN at screening, must have their potassium, and/or magnesium, and/or calcium replenished through supplementation and the levels must be within normal limits prior to the first dose of study drug.

A patient who has a laboratory test (peripheral blood test) results that do not satisfy the entrance criteria may have the tests repeated. These tests may be repeated as soon as the investigator believes the re-test results are likely to be within the acceptable range to satisfy the entrance criteria, but should be completed within approximately 2 weeks of the original screening visit date. In this case, the subject will not be required to sign another Informed Consent Form (ICF), and the original patient ID number assigned by the investigator will be used. In the event that the laboratory tests cannot be performed within the screening visit window, or the re-tests do not meet the entrance criteria, or other eligibility criteria have changed and are not met anymore, the patient is considered a screen failure, and must be discontinued from the study.

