8.5.3 Biomarkers

[figure not shown]
At the screening the selection of patient in each cohort will be based on the mutational status of T315I during screening as mentioned in the visit schedule [Table 8-1](#). Patient's BCR-ABL1 mutation status needs to be available and results have to be done within 6 months of screening. In addition, mutational analysis will be performed at screening to confirm the historical T315I mutational record if available.

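### Section 8.4.1 makes the screening T315I test conditional, and Sections 8.1 and 8.2 as visible do not require its result before cohort assignment or first dose

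*Protocol*

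**What the plan says.** Whether the screening test is done:

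- Section 8.4.1 provides for Sanger sequencing for T315I "at Screening if T315I mutational analysis is not confirmed", and again on confirmed loss of MMR and/or at end of treatment. It then refers the reader to Section 8.5.3.
- Inclusion criterion 4 sets no condition: "Mutation Analysis testing performed at screening".
- Section 8.5.3 asks for a BCR-ABL1 mutation status that "needs to be available and results have to be done within 6 months of screening". As a further step, "mutational analysis will be performed at screening to confirm the historical T315I mutational record if available".
- Table 8-3 lists "Blood for BCR-ABL1 Mutation analysis by Sanger Sequencing" at screening, 5 mL, with no condition or footnote.

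What must be known before allocation and dosing:

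- Section 8.5.3 says that cohort selection "will be based on the mutational status of T315I during screening".
- Section 8.1 states: "Screening assessments to confirm eligibility must be performed prior to randomization". It then singles out the RQ-PCR result, which "must be available prior to randomization and first dose of study treatment".
- Section 8.2 requires the central ECG reading and the RQ-PCR result before first dose.
- Section 8.1.1 places the eligibility check, and then treatment assignment through the IRT, after screening procedures are complete. It names no mutation result.

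**The concern.** T315I status is the allocation variable. Patients with the mutation go to Cohort C, and the others are randomized between A and B. It also sets the minimum number of prior TKIs (one or two, Inclusion 5) and whether strong CYP3A inhibitors are excluded (Exclusion 10).

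A site could rely on an older record in two ways. It could read 8.4.1 as waiving the test where status is already documented; Section 5 supports that reading, since it tells sites to use earlier medical records to confirm mutational status. Or it could draw the sample and assign the cohort before the result is back.

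The visible text gives no later correction by changing cohort. New T315I found on study means mandatory discontinuation (9.1.1), and escalation beyond the assigned doses is not permitted (6.5.1). After screening, sequencing takes place only on confirmed loss of MMR and/or at end of treatment, so a patient who never reaches MMR is next sequenced at end of treatment.

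**Working it through.** **1. The plan's own figure.** The sample size does not enter this point, but it reproduces. n = 1.96² × 0.18 × 0.82 / 0.12² = 39.4, rounded up to 40 evaluable; 40 / 0.9 = 44.4, rounded up to 45 enrolled. Nothing below changes it.

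**2. Is the test required in everyone?**

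| Place | Screening sequencing |
|---|---|
| Inclusion 4 | Every patient |
| 8.5.3 | Performed even where a historical record exists, in order to confirm it |
| Table 8-3 | 5 mL sample at screening, no condition |
| 8.4.1 | Only where status is not confirmed |

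The last row cannot be applied literally alongside the other three if a site regards a historical record as confirmation. The conflict lies wholly in current text. The stated purpose of Amendment 3, baseline mutation testing so that T315I acquired before study drug is not missed, shows which version was intended, but the conflict does not depend on it.

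**3. Must the fresh result be in hand?**

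- Section 8.1 uses two standards: eligibility assessments are to be *performed* before randomization, while the RQ-PCR result is to be *available* before randomization and first dose.
- Inclusion 4 is met once the test is performed. It does not depend on what the test shows.
- Inclusion 5 and 8.5.3 need a T315I status, but a record up to 6 months old can supply one.
- The RQ-PCR requirement does not cover sequencing. At screening, Table 8-3 lists separate samples: 20 mL for RQ-PCR and 5 mL for sequencing.
- The *performed* rule is tied to randomization, and Cohort C is assigned without randomization (6.3.2).

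So no visible sentence in 8.1 or 8.2 requires the new T315I result before assignment or dosing.

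**4. Dose that turns on the result** (Section 6.1.1).

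- Cohort A: 40 mg × 2 = 80 mg/day
- Cohort B: 80 mg × 1 = 80 mg/day
- Cohort C: 200 mg × 2 = 400 mg/day
- Ratio: 80 / 400 = 0.20

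**5. Oldest status that could govern.** This applies only if the fresh result is not used, and it reads the 6-month limit as counting back from screening.

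- SAP month length: 365.25 / 12 = 30.4375 days
- Six months: 6 × 30.4375 = 182.6 days
- Plus the 21-day screening window (8.1): 182.6 + 21 = 203.6, about 204 days at first dose
- With the 56-day window shown in the consent row of Table 8-1 instead: 182.6 + 56 = 238.6, about 239 days
- Fresh screening sample under the 21-day rule: at most 21 days

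**The case against.** The strongest reply is that the documents, read together, already settle the matter. Section 8.4.1 sends the reader to 8.5.3, where the screening test exists to confirm the historical record, so a record awaiting that test is arguably still unconfirmed. Omitting the test would breach Inclusion 4. An assessment meant to confirm eligibility is of no use without its result, and nobody would argue that lipase or bilirubin values need not be known before randomization merely because 8.1 does not list them. Section 8.1.1 holds back assignment until screening is complete. The relevant row of Table 8-1 may be redacted, and the IRT and laboratory manuals may contain the rule. Finally, 9.1.1 offers a managed access route to asciminib for patients with new T315I who lack reasonable alternatives.

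Part of this stands. A skipped test is unlikely, and the unseen manuals or redacted rows could require the result. Early failure can also shorten exposure to a wrong dose: no CHR at three months, or loss of CHR or MR2, ends treatment and can trigger sequencing before 24 weeks.

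The rest does not remove the point. The laboratory comparison fails because those criteria require a value within limits, whereas Inclusion 4 requires only that testing take place and an older record can supply the status. The cross-reference to 8.5.3 does not say which text prevails. Managed access comes after discontinuation and does not put right a starting dose that was wrongly allocated.

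**Conclusion.** The concern holds on both counts. Section 8.4.1 contradicts three other places on whether the screening T315I test is done in every patient. Sections 8.1 and 8.2, as visible, do not require its result before cohort assignment or first dose.

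What depends on the result is a five-fold difference in daily dose and the choice of cohort. The exposure is conditional: a site must either act on the 8.4.1 clause or assign without waiting. Only then could status up to about 204 days old govern. The documents give no rate of newly acquired T315I over such an interval and no rate of site departure, so the number of patients affected cannot be estimated and may be zero. No effect on a primary estimate or on the sample size is shown.

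This should be corrected because it concerns dose allocation and patient safety. It does not undermine the analysis. Confidence is medium, because the IRT and laboratory manuals and some redacted rows could not be examined.

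**What to change.** Two wording changes in the protocol:

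1. In 8.4.1, delete the conditional clause so that screening T315I sequencing applies to every patient, as in Inclusion 4, 8.5.3 and Table 8-3.
2. In 8.1 and 8.2, add the screening T315I sequencing result to the results required before cohort assignment and first dose. Word it to cover Cohort C assignment as well as randomization to A or B.

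A useful clarification, though not part of the defect, is to state which result governs when the historical record and the fresh test disagree.

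No new sample is needed, since the 5 mL draw is already scheduled. The cost is that allocation may wait for sequencing. The documents do not give the turnaround time, and it must fit within the 21-day screening window, so the sponsor should check this with the laboratory before making the change.

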8.4.2 Hematologic Response

Hematologic response assessments are to be done locally at the site. The hematology parameters required to be evaluated are listed in Table 8-6.

A complete hematologic response (CHR) is defined as all of the following present for ≥ 4 weeks:

[figure not shown]
- WBC count <10 x 10⁹/L
- Platelet count <450 x 10⁹/L
- Basophils <5%
- No blasts and promyelocytes in peripheral blood
- Myelocytes + metamyelocytes < 5% in peripheral blood
- No evidence of extramedullary disease, including spleen and liver

[figure not shown]
Loss of CHR

Loss of CHR is defined if patients exhibit:

- WBC count >10 x 10⁹/L
- Platelet count >450 x 10⁹/L
- Basophils >5%
- Any blasts and promyelocytes in peripheral blood
- Myelocytes + metamyelocytes > 5% in peripheral blood

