8.3 Safety and tolerability

Safety assessments are specified below with the assessment schedule detailing when each assessment is to be performed.

Significant findings that were present prior to the signing of informed consent must be included in the Relevant Medical History/Current Medical Conditions page on the patient's eCRF. Significant new findings that begin or worsen after informed consent must be recorded on the AE page of the patient's eCRF.

For details on AE collection and reporting, refer to AE section.

Table 8-4 Assessments

| Assessment | Specification |
|----------------------|---|
| Physical examination | 
A complete physical examination will include the examination of general appearance, skin, neck (including thyroid), eyes, ears, nose, throat, lungs, heart, abdomen, back, lymph nodes, extremities, vascular and neurological. Information about the physical examination must be present in the source documentation at the study center and will be collected on the following visits as specified in Table 8-1 :
 
Screening Week 1 Day 1, Week 4
 
With the exception of Weeks 12, 24, 36, 48 and 72, Physical examination can be omitted for the remainder of the protocol. Significant findings that were present prior to the signing of informed consent must be included in the Medical History page on the patient's eCRF. Significant new findings that begin or worsen after informed consent must be recorded on the Adverse Event page of the patient's eCRF. Presence of extramedullary leukemic involvement will be checked with each physical examination as outlined above. Findings on physical examination consistent with extra-medullary leukemic involvement will be recorded (e.g. liver and spleen size, any other organ involvement).
 |
| Vital signs | 
Vital signs include blood pressure (supine position preferred when ECG is collected), pulse measurement, and body temperature and must be performed at the following visits as specified in Table 8-1:
 
 • Screening |

| Assessment | Specification |
|-------------------|--|
| | 
 • Week 1 Day 1 • Week 2 Day 1 • Week 4 
With the exception of Weeks 12, 24, 36, 48 and 72, Vital Signs can be omitted if for the remainder of the protocol
 |

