## 1.2 Study objectives and endpoints

**Table 1-1      Objective(s) Endpoint(s)**

Primary Objective(s)	Endpoint(s) for primary objective(s)

• To evaluate safety profile of monotherapy asciminib in CML- CP in 3L and beyond, for Cohorts A and B

	

• AEs, SAEs and laboratory evaluation for 24 Weeks.

Secondary Objective(s)	Endpoint(s) for secondary objective(s)

• To evaluate safety profile of monotherapy asciminib in CML- CP in 3L and beyond, for Cohort C

• To evaluate safety profile of monotherapy asciminib in CML- CP in all Cohorts A, B and C

• To estimate the rate of patients with hematologic and molecular response by specific time points for Cohort A, B and C

• To estimate the rate of patients with deep molecular response by specific time points for Cohort A, B and C

• To estimate time to hematologic and molecular response

• To evaluate the duration of hematologic and molecular response

• To Evaluate the progression free survival (PFS)

• To Evaluate Overall Survival (OS)

	

• AEs, SAEs and laboratory evaluation for Cohort A, Cohort B and Cohort C, during 48, 72 weeks

• Rate of CHR, MR2, MMR, by 12, 24, 48, 72 weeks of therapy

• Rate of MR4, MR4.5 by 48, 72 weeks of therapy

• Time to CHR, MR2, MMR, MR4, MR4.5

• Duration of CHR, MR2, MMR, MR4 and MR4.5

• PFS during 24, 48 and 72 weeks

• OS during 24, 48 and 72 weeks

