### **Duration of CHR, MR2, MMR, MR4 and MR4.5**

Duration of Response (DOR) is the time from the date of the first documented molecular (MR2, MMR, MR4, MR4.5) or Hematologic (CHR) response to the date of first documented loss of that response or death due to any cause or progression to AP/BC, whichever occurs first.

The start date is the date of first documented response and the end date is defined as the date of the first documented loss of that response or death due to any cause or progression to AP/BC. Participants continuing without that event will be censored at the date of their last adequate molecular or hematologic response assessment.

DOR for each response level will be analyzed using the Kaplan-Meier Product-Limit method.

Estimates of DOR at specific timepoint and the 25th, median and 75th percentile of the DOR and their 95% confidence intervals will be provided, if applicable.

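### The Loss of CHR list omits the extramedullary, spleen and liver condition that CHR requires, so a response that fails only on examination has no end event for CHR duration at that date

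*Protocol*

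**What the plan says.** Protocol 8.4.2 sets an all-of rule: "A complete hematologic response (CHR) is defined as all of the following present for ≥ 4 weeks". Five conditions concern the blood count and differential. The sixth is "No evidence of extramedullary disease, including spleen and liver". SAP 2.8.2 repeats all six.

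The next paragraph of Protocol 8.4.2 begins "Loss of CHR is defined if patients exhibit" and then takes the five blood conditions in the same order. Its last entry is "Myelocytes + metamyelocytes > 5% in peripheral blood", after which Section 8.5 starts. There is no examination item.

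The SAP objectives table lists "Duration of CHR, MR2, MMR, MR4 and MR4.5" among the secondary endpoints, as does Protocol Table 2-1. SAP 2.8.2 measures duration from the first documented molecular "or Hematologic (CHR) response to the date of first documented loss of that response or death due to any cause or progression to AP/BC", whichever is first. A patient without such an event is censored at the last adequate response assessment. SAP 5.3.1 defines loss of MR2 and loss of MMR, but not loss of CHR.

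The examination data are collected. Protocol Table 8-4 states: "Presence of extramedullary leukemic involvement will be checked with each physical examination as outlined above". It asks for liver and spleen size to be recorded, and Table 8-1 marks extramedullary involvement as a database item.

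**The concern.** A duration endpoint is interpretable when the event that closes it matches the state that opened it, or when any difference is stated and justified. Here one of six opening conditions has no closing counterpart, and no reason is given. The affected patient is out of CHR by one list and has not lost CHR by the other.

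At stake is the Kaplan-Meier estimate of CHR duration in each cohort. If such a patient goes on to a later event, that event is dated too late. If the patient is censored instead, possibly because treatment stopped when the response failed, the censoring is informative. Both push the estimate towards longer duration.

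Protocol 9.1.1 adds an inconsistency. It makes both loss of CHR and the absence of CHR at three months or later grounds for treatment failure. The same patient can meet the second ground without meeting the first.

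**Working it through.** The plan states no figure on this point, so there is none to reproduce. The check is a comparison of the two lists, then a test patient, then a sensitivity range.

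**Step 1. The lists side by side (Protocol 8.4.2).**

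| Component | CHR requires | Loss of CHR list |
|---|---|---|
| White cells (×10⁹/L) | below 10 | above 10 |
| Platelets (×10⁹/L) | below 450 | above 450 |
| Basophils | below 5% | above 5% |
| Blasts and promyelocytes in blood | none | any |
| Myelocytes plus metamyelocytes | below 5% | above 5% |
| Extramedullary disease, spleen, liver | none | no entry |

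Five of the six components have a counterpart. A value exactly on a limit, such as white cells of 10, meets neither list.

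**Step 2. A test patient.** Take a patient in CHR who now has white cells 7, platelets 250, basophils 1%, no blasts, promyelocytes, myelocytes or metamyelocytes, and new extramedullary disease.

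- CHR: the sixth condition fails, so the patient is not in CHR.
- Loss of CHR as written: none of the five entries is met, so there is no loss.
- Accelerated phase (Protocol 9.1.1): the criteria are blasts, blasts plus promyelocytes, basophils, and thrombocytopenia unrelated to therapy. None is met.
- Blast crisis (Protocol 9.1.1): the criterion is at least 30% blasts. It is not met.
- End event under SAP 2.8.2 at this date: none.

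With the sixth item added to the loss list, loss is recorded at this examination.

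**Step 3. Possible size.** The documents give no rate, so the share is an assumption. Let f be the share of all true CHR end events that are seen on examination only and go uncounted. Assume constant hazards, and that affected patients are either censored or continue with the same hazard of a counted event. The counted hazard is then (1 − f) times the true one, so:

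- reported median ÷ true median = 1/(1 − f)
- reported event-free proportion = (true proportion)^(1 − f)

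| f | Median ratio | A true 90% event-free is reported as |
|---|---|---|
| 0% | 1.00 | 90.0% |
| 2% | 1.02 | 90.2% |
| 5% | 1.05 | 90.5% |
| 10% | 1.11 | 91.0% |

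For scale, suppose all 45 patients of Cohort A or B entered this analysis. The 95% half-width around 90% would be 1.96 × √(0.9 × 0.1/45) = 0.088, or about 9 percentage points. If 10% of the 45 lost CHR (4.5 patients), a 10% share of those losses would be 0.45 of a patient.

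**The case against.** The strongest reply is that a loss rule need not mirror its response rule. Loss of MMR in this plan deliberately does not: it needs a rise above 0.1%, a rise of at least 5-fold from the lowest value, and confirmation. Leaving the examination item out of CHR loss might also have been a choice. It is fair that a mismatch alone proves nothing. But the MMR asymmetry is spelled out, while nothing in either document indicates that the CHR omission was intended.

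Four stronger readings are tempting, and the documents do not support them:

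- *The failure is never an event.* Counts that later cross a limit, progression to AP/BC, or death still end the duration, only later. The 9.1.1 criterion on absence of CHR at three months or later may also take the patient off treatment. That does not repair the endpoint, because treatment failure is not an end event in SAP 2.8.2.
- *The finding goes unrecorded.* It is recorded; it is not counted as a loss.
- *CHR duration as a whole can only be too long.* That direction belongs to this omission. Loss of CHR requires no confirmation or minimum duration and states no any/all rule, so a single transient count could also end CHR early.
- *Such losses are to be expected because inclusion criterion 3 admits hepatosplenomegaly.* A patient who enters with it is not in CHR until it resolves. That says nothing about new organ enlargement with normal counts after CHR.

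Two practical objections remain. Physical examination may be omitted at many visits after Week 4, so examination-based losses would be dated coarsely. It may not be omitted at Weeks 12, 24, 36, 48 and 72, which are the time points for hematologic response in SAP Table 2-2, so the objection limits precision but does not defeat the change. And editing the list in Protocol 8.4.2 would alter a discontinuation trigger and need an amendment, which is why the analysis definition belongs in the SAP.

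**Conclusion.** The gap is real. As written, a patient in CHR who develops extramedullary, spleen or liver involvement with normal counts no longer meets CHR and has no end event at that date. No other section of either document supplies one. For this omission the bias is towards longer CHR duration; the net bias of the full loss definition is not established.

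The size is unknown and may be nil or small. The range of 1.00 to 1.11 for the median ratio rests on an assumed share of 0-10% and on constant hazards. Even at the top of that range the shift in a 90% event-free proportion is about 1 point, well inside the sampling error of a cohort of 45. The endpoint is secondary, descriptive and untested, and the primary safety analysis does not depend on it. This should be corrected because the rule gives a wrong answer for an identifiable patient and the remedy is cheap; it does not threaten the trial's main conclusions.

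**What to change.** In SAP 2.8.2 or 5.3.1, define loss of CHR for the duration endpoint as the first response assessment at which any of the six CHR components no longer holds. Include the extramedullary/spleen/liver item already held in the database. Set the limits to complement the CHR definition (for example, white cells of 10 or more), so that no value falls between the two. The word any also settles the missing any/all rule. Record the definition in SAP Section 4, which now declares no change from the protocol. If the sponsor means to leave the examination item out, the SAP should say so and give the reason.

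The cost is a short SAP amendment and some programming, with no new procedure. Examination-based losses can be dated only at visits with a physical examination (at least Weeks 12, 24, 36, 48 and 72), and reported durations may come out slightly shorter.

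Separately, Protocol 9.1.1 uses both loss of CHR and absence of CHR at three months or later for discontinuation, and the two can disagree for the same patient. The sponsor must reconcile 8.4.2 and 9.1.1. No clinical rule is proposed here.
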